6.5 Dose Modification

Dose modifications and stopping criteria for RXC004 are detailed in Section 6.5.1.

For participants in Module 3 (RXC004 in combination with pembrolizumab): Dose modifications and stopping criteria for pembrolizumab are detailed in Appendix L. If either agent is interrupted or discontinued for a related AE, the other agent (pembrolizumab or RXC004) may be continued if the patient is judged (by the investigator) to be receiving clinical benefit.

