8.3.1 Time Period and Frequency for Collecting AE and SAE Information

Adverse Events (and Events of Clinical Interest for pembrolizumab) will be collected from time of signature of main study informed consent form throughout the treatment period and until the 30 days after last dose of RXC004 (for patients treated with RXC004 monotherapy) or 90 days after the last dose of pembrolizumab (for patients treated with RXC004 and pembrolizumab combination therapy), or 30 days following cessation of pembrolizumab treatment if the participant initiates new anticancer therapy, whichever is earlier.

SAEs will be recorded from the time of signing of main study informed consent form.

If the investigator becomes aware of an SAE with a suspected causal relationship to the investigational medicinal product that occurs after the end of the clinical study in a participant treated by him or her, the investigator shall, without undue delay, report the SAE to the sponsor.

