9.4.2.3 Tertiary/Exploratory Endpoint(s)

9.4.3 Safety

9.4.3.1 Adverse Events

Treatment-emergent AEs (TEAEs) are defined as AEs with an onset after dosing and pre-existing AEs that worsen after the start of dosing and within 30 days of stopping RXC004 monotherapy, or 90 days after the last dose of pembrolizumab (for patients in Module 3), or 30 days following cessation of pembrolizumab study treatment if the patient initiates new anticancer therapy, whichever is earlier. For AEs, verbatim terms in the CRF will be mapped to preferred terms and system organ class using the Medical Dictionary for Regulatory activities (version 22.0 or later). CTCAE criteria v5.0 will be used to grade the severity of AEs. The incidence of TEAEs will be summarised by preferred term and system organ class as well as severity. Treatment-related TEAEs will be summarised in the same way. Per-patient incidence of SAEs will also be produced.

By patient, listings of all AEs, deaths, SAEs and TEAEs leading to discontinuation will also be produced.

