#### 4.12.1 Adverse Events

Adverse Events will be collected from time of signature of informed consent form throughout the treatment period and until 30 days after the last dose of RXC004.

SAEs will be recorded from the time of signing of main study informed consent form until the follow-up period is completed: 30 days after the last dose of RXC004 for patients treated with RXC004 monotherapy only) or 90 days after the last dose of Pembrolizumab (for patients treated with RXC004 and Pembrolizumab).

The following variables will be collected for each AE:

- AE (verbatim)
- Start/Stop date
- NCI CTCAE grade at onset and grade changes
- Seriousness
- Investigator causality rating against the Investigational Product(s)
- Action taken with regard to Investigational Product(s)
- Action taken with regards to AE
- Outcome

In addition, the following variables will be collected for SAEs:

- Date AE met criteria for SAE
- Date Investigator became aware of SAE

- Death
- Hospitalisation
- Life threatening
- Congenital anomaly or birth defect
- Disability or permanent damage
- Other medically important serious event
- Date of hospitalisation
- Date of discharge
- Causality assessment in relation to study procedure(s)
- Causality assessment to other medication

Partially complete AE dates will not be imputed in the listings and the available day, month and year components will be used to determine if an adverse event is treatment-emergent taking the first dosing date and last treatment date as references.

More specifically:

- Start date of AE missing: Assumed to be date of first treatment dose.
- Start day and month of AE missing: Assumed to be date of first treatment dose (if same year for both dates), January first otherwise.
- Start day of AE missing: Assumed to be date of first treatment dose (if same month and year for both dates), first day of the month otherwise.
- End date for non-ongoing AE missing: Assumed to date of last treatment dose
- End day and month for non-ongoing AE missing: Assumed to be date of last treatment dose (if same year for both dates), December 31st otherwise.
- End day for non-ongoing AE missing: Assumed to be date of last treatment dose (if same month and year for both dates), last day of the month otherwise.

Treatment-emergent adverse events (TEAEs) with missing relationship to the study drug will be considered as related.

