AEs will be coded using the Medical Dictionary for Regulatory Activities (MedDRA), latest version. Grading will be performed using NCI CTCAE version 5.0.

TEAEs are defined as those AEs with an onset after dosing and those pre-existing AEs that worsen after the start of dosing and within 30 days of stopping RXC004.

An overview table of TEAEs will be provided showing the number of patients, the percentage of patients and the number of events for the following categories of events:

- Any TEAE
- Any serious TEAE (STEAE)
- Any treatment related TEAE
- Any serious TEAE related
- Any TEAE leading to permanent discontinuation of RXC004
- Any TEAEs leading to RXC004 reduction
- Any TEAEs leading to RXC004 interruption

For TEAEs, TEAEs considered related, STEAEs, STEAEs considered related, TEAEs leading to study treatment discontinuation, TEAEs leading to RXC004 reduction, TEAEs leading to RXC004 interruption, TEAEs by maximum grade, TEAEs with grade  $\geq 3$ , TEAEs with grade  $\geq 3$  related, death, detailed tables will be created showing the number of patients who experienced at least one TEAE, the corresponding percentage of patients and the number of events by SOC and PT.

For module 1 and 2, AE relatedness corresponds to a relation to RXC004. For Module 3, AE relatedness corresponds to at least one of RXC004/pembrolizumab relation.

For all AE summaries, SOC will be sorted by alphabetical order. PTs, within each SOC, will be sorted by descending order of total frequency. In the event of PTs with equal total frequencies, the relevant PTs will be sorted alphabetically. In addition, a table summarizing TEAEs by decreasing frequency of Preferred Terms will be produced for all TEAEs and TEAEs related.

A table will also be produced showing the details for every patient that die (death date, cause of death etc...).

Listing of all AEs (including non-treatment-emergent events) will be provided. This listing will be presented, ordered by patient. It will include patient identifier, AE (SOC, PT, and verbatim term), date of onset, date of resolution, duration, maximum grade, seriousness, action taken, outcome and causality.

In addition, data related to dysgeusia examination questionnaire will be listed. The data will also be summarized as categorical data providing there are enough data to make it meaningful to do so.

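### SAP 4.12.1 ends the TEAE window 30 days after RXC004 in all modules, without the pembrolizumab-based Module 3 limit in the protocol

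*SAP*

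**What the plan says.** **SAP 4.12.1.** One TEAE definition serves all modules: events starting after dosing, and "those pre-existing AEs that worsen after the start of dosing and within 30 days of stopping RXC004". AE collection runs from consent "throughout the treatment period and until 30 days after the last dose of RXC004", also without a module split. Two other parts of the section are adapted to the combination:

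- SAE recording continues to 30 days after RXC004 for monotherapy, "or 90 days after the last dose of Pembrolizumab (for patients treated with RXC004 and Pembrolizumab".
- On causality: "For Module 3, AE relatedness corresponds to at least one of RXC004/pembrolizumab relation".

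The incidence tables listed there (all, related, serious, Grade 3 or higher, and those leading to action on treatment) are tables of TEAEs.

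**Protocol.** Section 9.4.3.1 sets the TEAE limit "within 30 days of stopping RXC004 monotherapy, or 90 days after the last dose of pembrolizumab (for patients in Module 3", cut to 30 days after pembrolizumab cessation if new anticancer therapy begins, whichever is earlier. Section 8.3.1 ends AE collection in combination patients at "90 days after the last dose of pembrolizumab (for patients treated with RXC004 and pembrolizumab combination therapy", with the same cut. Section 6.5 covers the case where one drug is stopped because of toxicity attributed to it: "the other agent (pembrolizumab or RXC004) may be continued if the patient is judged (by the investigator) to be receiving clinical benefit".

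**Relation between the two.** SAP Section 1 says that it is based on Protocol Version 6, which contains Module 3. The readable entries in SAP 4.16 (changes from the protocol) do not mention the TEAE window. One entry there is redacted.

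**The concern.** In Module 3 the two documents tie the window to different drugs. The SAP counts an event as related if either drug is implicated, but closes the window by RXC004 alone. It also records SAEs to 90 days after pembrolizumab, then tabulates only those SAEs that are TEAEs, so SAEs from that later period are recorded but not counted in its serious-TEAE tables.

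The events at risk are late ones. Appendix L 1 of the protocol warns that immune-related events can appear several months after pembrolizumab ends, and protocol 12.3.1 names colitis as the toxicity that the two drugs share. Pembrolizumab alone is also a foreseen course. Four RXC004 stopping rules in Table 11 let it continue: Grade 2 dysgeusia with more than 20% weight loss, fragility fracture, bone density loss above 7%, and a β-CTX rise. For such a patient the SAP window can close while study treatment is still being given. At stake is how completely the tables describe the safety of a combination that, according to protocol 12.3.1, had not been given before.

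**Working it through.** The plan gives no figure to reproduce. The check compares the two end dates.

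**Inputs.** r = day of last RXC004 dose; p = day of last pembrolizumab infusion; infusions every 42 days (protocol 12.7.1).

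- SAP end = r + 30 (SAP 4.12.1).
- Protocol end = p + 90, or p + 30 if new anticancer therapy starts (protocol 9.4.3.1), taking cessation as the last infusion.
- Gap = protocol end − SAP end. That is 60 + (p − r) without new therapy, and p − r with it.

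**Results.**

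| Situation | New therapy | Gap in days |
|---|---|---|
| Both drugs stop together, p = r | no | 60 |
| RXC004 stops 0 to 41 days after the last infusion | no | 60 − 0 = 60 down to 60 − 41 = 19 |
| One further infusion after RXC004 stops, p − r = 1 to 42 | no | 61 to 102 |
| Two further infusions, p − r = 43 to 84 | no | 103 to 144 |
| Pembrolizumab does not outlast RXC004, p ≤ r | yes | none lost |
| Pembrolizumab outlasts RXC004, p > r | yes | p − r |

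**Window closing during treatment.** The SAP window ends before the last infusion when p − r exceeds 30. With two further infusions this always happens: the minimum p − r is 43, so the window ends at least 43 − 30 = 13 days before that infusion on nominal dates.

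**Example.** RXC004 stops on day 42 and the last infusion is on day 85. The SAP window ends on day 42 + 30 = 72. The protocol window ends on day 85 + 90 = 175, a gap of 103 days. With new therapy the protocol window ends on day 85 + 30 = 115, a gap of 43 days.

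**Does the protocol clause lose anything the SAP has?** Sometimes, when RXC004 outlasts pembrolizumab. Without new therapy, p + 90 falls before r + 30 once r − p exceeds 60; for r − p = 91 the shortfall is 91 − 60 = 31 days. With new therapy, p + 30 falls r − p days before r + 30, which is 0 to 41 days within one infusion interval. This is the reason for the optional floor in the fix.

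**The case against.** **The wording.** The 30-day phrase could attach only to pre-existing events that worsen, leaving new-onset events without a limit. The SAP also judges emergence for partial dates against the last treatment date, not the last RXC004 date. The ambiguity is real but does not remove the conflict. Worsening events would still be cut at RXC004 plus 30 days. New-onset events would have no end date, whereas protocol 9.4.3.1, read naturally, bounds both kinds. The partial-date rule does not redefine the window for complete dates.

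**The consequence is limited.** This stands in large part. Protocol 8.3.1 governs what sites collect, the SAP lists all AEs including non-emergent ones, deaths have their own table, and protocol 9.4.3.1 plans per-patient SAE incidence. A listing still gives no incidence.

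**The largest gaps need unusual patients.** Also fair. Median PFS on pembrolizumab alone was 1.8 and 2.0 months in the two earlier studies (protocol 2.2.4.4), and two further infusions require at least 43 nominal days on pembrolizumab after RXC004 stops. Death can also cut a gap short.

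**Section 6.6.** It uses 30 days for Module 3 AEs and allows pembrolizumab alone, but it concerns patients still on treatment at the data cut-off. It neither supports the SAP window nor shows how often the window would close during treatment.

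**Conclusion.** The SAP departs from the protocol on the Module 3 TEAE limit and AE collection period, and should be corrected. Without new anticancer therapy, its window closes 60 days early if both drugs stop together, 19 to 60 days early if RXC004 stops within one infusion interval after the last infusion, and more than 60 days early if pembrolizumab continues alone. With new therapy and pembrolizumab not outlasting RXC004, nothing is lost. These figures assume that the 30-day limit applies to both new-onset and worsening events. The number of patients affected cannot be computed from the documents, and short PFS makes the largest gaps uncommon.

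A reader might infer more, but the documents do not support it:

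- *Every Module 3 patient loses 60 days.* The gap depends on which drug stopped last and on new therapy, and can be nil.
- *Late events will not be collected.* The protocol sets collection, and its Table 18 already schedules follow-up 30 days after RXC004 and 90 days after pembrolizumab.
- *The change was left undeclared.* One entry in SAP 4.16 is redacted, so this cannot be shown.
- *SAE recording or the protocol must also change.* The SAP's SAE sentence already runs to 90 days after pembrolizumab, and the protocol already has a Module 3 limit.

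**What to change.** In SAP 4.12.1:

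1. Put the Module 3 clause of protocol 9.4.3.1 into the TEAE definition, and state that the limit applies to both new-onset and worsening AEs.
2. Put the matching clause of protocol 8.3.1 into the AE collection sentence.
3. Optionally, in the SAP only, add that the Module 3 TEAE window ends no earlier than 30 days after the last RXC004 dose, and list this in SAP 4.16. It protects the RXC004 follow-up period when RXC004 outlasts pembrolizumab.

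Leave the 90-day SAE recording sentence as it is. Applying the new-therapy cut to it would reduce SAE recording from 90 to 30 days where both drugs stop together. Make no protocol amendment: none is needed, and Appendix A 1 would require ethics and regulatory approval.

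The cost is two SAP sentences and minor programming. The last-dose dates of both drugs are already needed for the exposure summaries in SAP 4.10, and no visits are added.

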2.3.1.2 Risks of RXC004-Associated AEs

As described in section 4.4.1, RXC004 has been evaluated as a monotherapy in 23 patients in a Phase 1 monotherapy dose-escalation trial at doses of 0.5-10mg QD, in which doses of up to 2 mg QD were found to be tolerable and safe.

At doses up to and including 2 mg QD, the most common TRAEs of any grade were fatigue (10/20; 50%), nausea (7/20; 35%), anorexia (6/20 patients), dysgeusia (6/20; 30%) and vomiting (4/20; 20%).

Dysgeusia Events

In the Phase 1 study, RXC004-related dysgeusia was observed in 6/20 (30%) patients who received doses of up to 2 mg QD; 3/4 patients (75%) receiving 3 mg QD; and by the single patient (100%) who received 10 mg QD. This study protocol includes an assessment for the further characterisation of this event, and includes guidance for the management of dysgeusia (Appendix J). Guidance for dose modifications of RXC004 for all toxicities are provided in Section 6.5.

Colitis Events

In the Phase 1 study, events of intestinal inflammation (colitis, enteritis or enterocolitis) were observed in four patients who started treatment with RXC004 at doses of ≥ 3 mg QD and three were dose-limiting toxicities. CTCAE Grade 3 RXC004-related colitis occurred in the single patient who received 10 mg and CTCAE Grade 3 enteritis occurred in one patient who received RXC004 3 mg QD. CTCAE Grade 2 colitis also developed in two more patients who started treatment with 3 mg RXC004, both Grade 2 events presented during Cycle 2. Symptoms included abdominal pain, intermittent constipation, diarrhoea, nausea and/or vomiting. Blood and mucus in the stool were not apparent in any of the cases. Symptoms were usually accompanied by, and preceded by, a raised CRP. In two patients, the event recurred after initially responding to steroids, but responded again to further treatment.

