3mg QD	4	4	Non-tolerated dose RXC004 related AEs ≥ CTCAE G2 (4/4 patients); G2 Fatigue (1/4 patients) ^b G2 Nausea (1/4 patients) ^b G2 Constipation (1/4 patients) ^b G2 Anorexia (2/4 patients) ^b G2 Colitis (2/4 patients) ^b [DLT] G2 Dysgeusia (1/4 patients) ^b G3 Enteritis (1/4 patients) [DLT] G2 hyponatremia (1/4 patients) G2 Humerus fracture (1/4 patients) G5 Subdural Hematoma (1/4 patients)
10mg QD	1	1	Non-tolerated dose One DLT – G3 Diarrhoea. G3 proctitis, G2 enterocolitis, dysgeusia and fragility bone fractures also reported for this patient

^a The DLT assessment period runs from the start of dosing with RXC004 (Cycle 0 Day 1) up to Cycle 1 Day 21. To be evaluable for DLT assessment patient must had received at least 66% of the intended dose of RXC004 during Cycle 1 or have experienced a DLT event in the assessment period

^b The start date of one or more events was outside of the DLT period. However, AEs occurring in Cycle 2 and beyond which meet the definition of a DLT or are considered clinically significant may also be considered by the Safety Review Committee, when making dose escalation decisions.

AE, adverse event; DLT, dose-limiting toxicity; QD, once daily.

No DLTs were observed in the patients dosed in the first three cohorts since the study was restarted (RXC004 doses from 0.5mg to 2mg). At the 3mg dose level, two DLTs of colitis and enteritis were observed in 2/4 (50%) evaluable patients, which led to the SRC declaring RXC004 3 mg QD as non-tolerated.

Denosumab (XGEVA™ - 120 mg s.c. once every month) was administered prophylactically from Cycle 0 to all patients from cohort 3 (1.5mg RXC004) onwards, to maximise bone safety.

A summary of the TEAEs, regardless of causality, reported for RXC004 monotherapy in the Phase 1 study RXC004/0001 (NCT03447470) up to 30 July 2021 is included in Table 2 below.

Table 2 Summary of TEAEs (Phase 1 study RXC004/0001, monotherapy)

Number of patients with TEAE	0.5 mg; N=4 n (%)	1.0 mg; N=3 n (%)	1.5 mg; N=7 n (%)	2.0 mg; N=6 n (%)	3.0 mg; N=4 n (%)	10.0 mg; N=1 n (%)	Overall; N=25 n (%)
Any TEAE	4 (100)	3 (100)	7 (100)	6 (100)	4 (100)	1 (100)	25 (100)
Any Treatment-Related TEAE	4 (100)	3 (100)	5 (71)	5 (83)	4 (100)	1 (100)	22 (88)
TEAE \geq Grade 3	0 (0)	1 (33)	6 (86)	1 (17)	3 (75)	1 (100)	12 (48)
Treatment-Related TEAE \geq Grade 3	0 (0)	0 (0)	2 (29)	1 (17)	1 (25)	1 (100)	5 (20)
Serious TEAE	0 (0)	1 (33)	5 (71)	1 (17)	3 (75)	1 (100)	11 (44)

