6.5.1 Dose Modifications for RXC004

RXC004 dose reduction and interruption are permitted.

RXC004 may be dose interrupted (withheld) until a clinically significant (any grade) and/or a grade ≥ 3 related adverse event resolves to baseline or \leq grade 2. RXC004 may also be withheld if it is necessary to give a concomitant medication that is a moderate or strong CYP3A4 inhibitor.

Colitis events may occur with RXC004 or with pembrolizumab, and should be managed per Appendix K and, for participants in Module 3, the dose modification and toxicity management guidelines for irAEs associated with pembrolizumab (Appendix L 1) if applicable. For patients receiving the combination treatment with RXC004 and pembrolizumab, the most conservative guideline should be followed.

RXC004 dose interruption and stopping criteria are detailed in Table 11.

Table 11 RXC004 Dose Modification and Stopping Criteria

Event	Action
Colitis events (e.g. Colitis, ileitis, enterocolitis etc)	
Grade 1	Reduce RXC004 to a lower dose (see Table 12 for dose reduction scheme) and manage per Appendix K. If receiving RXC004 in combination with pembrolizumab, no additional action is required for pembrolizumab.
Grade 2	Interrupt RXC004. Manage as per Appendix K. When event has resolved to Grade $\leq 1^a$ and steroids have been tapered to prednisolone ≤ 10 mg per day (or equivalent), resume RXC004 at a lower dose (see Table 12 for dose-reduction scheme). If event recurs after re-starting study treatment, then RXC004 should be permanently discontinued. If receiving RXC004 in combination with pembrolizumab, interrupt pembrolizumab and see Appendix L for guidance.
Grade 3	Interrupt RXC004. Manage as per Appendix K. When event has resolved to Grade $\leq 1^a$ and steroids have been tapered to ≤ 10 mg of prednisolone per day (or equivalent), resume RXC004 at a lower dose (see Table 12 for dose reduction scheme). If event recurs after re-starting study treatment, then RXC004 should be permanently discontinued. If receiving RXC004 in combination with pembrolizumab; permanently discontinue both agents and manage as per Appendix K and Appendix L.
Grade 4	If receiving RXC004, either as monotherapy or in combination with pembrolizumab: Permanently discontinue both agents. Manage per Appendix K and Appendix L.
Dysgeusia events	

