8.3.13 AEs of Potential Interest (AEPI)

As discussed in Section 2.3.1, colitis events and bone toxicity events are classified as AEPIs for RXC004. This means that additional information will be captured on the CRF for any CTCAE-preferred terms that fall into these categories. These terms will be defined in the CRF Guidelines and reviewed at any update of the CTCAE definitions.

Events of Clinical Interest for pembrolizumab are described in Section 12.10.

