**REVISION HISTORY**

Version No.	Effective Date	Summary of Change(s)
1.0	22-Jul-2021	New document
2.0	25-Jan-2022	SMC meeting Revision of Adverse Events section (Outputs added, AEPI, Dysgeusia assessment) Add CCI [REDACTED] Add eDISH plots Add Dysgeusia evaluation
3.0	21-Sep-2023	Add new variables in Baseline Characteristics Revision of RDI definitions Revision of sorting rules for AEs and ConMeds Add CCI [REDACTED] analysis
4.0	15-Feb-2024	Revision Objectives endpoints definition Revision Evaluable Set definition Revision Concomitant Medications imputation rules Add CCI [REDACTED] imputation rules Add Labs BLQ rules

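### SAP 4.12.1 plans no grouped per-patient summary of colitis events or bone toxicity events, although the protocol defines and collects both as multi-term adverse events of potential interest

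*SAP*

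**What the plan says.** Protocol 8.3.13 states that "colitis events and bone toxicity events are classified as AEPIs for RXC004" and that "additional information will be captured on the CRF for any CTCAE-preferred terms that fall into these categories". The term lists themselves are left to the CRF Guidelines. The dose-modification table (Protocol 6.5.1, Table 11) has one block for "Colitis events (e.g. Colitis, ileitis, enterocolitis etc", so the harm is managed as a group as well. The risk section (Protocol 2.3.1.2) reports Phase 1 in the same grouped way.

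The analysis text works at a different level. Protocol 9.4.3.1 says: "The incidence of TEAEs will be summarised by preferred term and system organ class as well as severity". SAP 4.12.1 plans an overview table, then a set of detailed tables (all, related, serious, leading to dose action, by maximum grade, Grade 3 or higher), each giving the number of patients, "the corresponding percentage of patients and the number of events by SOC and PT". It adds a table ordered by preferred-term frequency, a table of deaths and a by-patient listing. The overview has no AEPI row. The section, which is not redacted, contains no AEPI term list, no grouped incidence and no worst grade by group. Dysgeusia, by contrast, has its own section (SAP 4.12.2).

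**The concern.** When one clinical harm can be recorded as colitis, enteritis, enterocolitis, ileitis or proctitis, a table by preferred term divides the affected patients among several small rows. The question a safety reader asks is how many patients had the harm and how bad it was, and no row answers it. Colitis and enteritis are the events that led to 3 mg being declared non-tolerated in Phase 1 (Protocol 4.4.1.1), and colitis is the one overlapping toxicity named for the pembrolizumab combination (Protocol 12.3.1). In small cohorts, one or two patients moving between rows changes the picture. With 25 patients, each patient is 1/25 = 4 percentage points.

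**Working it through.** **Inputs** (Protocol 2.3.1.2 and 4.4.1.1, Table 1)
- Patients dosed: 4 + 3 + 7 + 6 + 4 + 1 = 25. No colitis events were seen in Phase 1 at starting doses of 2 mg or lower.
- At 3 mg: Grade 2 colitis in two patients and Grade 3 enteritis in one. Section 2.3.1.2 makes clear that these are three different patients.
- At 10 mg, one patient. Table 1 records "One DLT – G3 Diarrhoea. G3 proctitis, G2 enterocolitis, dysgeusia and fragility bone fractures also reported for this patient". Section 2.3.1.2 records the same patient as Grade 3 colitis.

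**Reproducing the plan's figure.** 2 + 1 + 1 = 4 distinct patients, which agrees with the protocol's statement that "events of intestinal inflammation (colitis, enteritis or enterocolitis) were observed in four patients".

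**The same four patients shown by single term.** The right-hand column takes colitis as the 10 mg patient's only term.

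| | 10 mg case as in Table 1 | 10 mg case as in Section 2.3.1.2 |
|---|---|---|
| Colitis | 2 | 3 |
| Enteritis | 1 | 1 |
| Enterocolitis | 1 | 0 |
| Proctitis | 1 | 0 |
| Sum of rows | 5 | 4 |
| Patients, grouped | 4/25 = 16.0% | 4/25 = 16.0% |
| Largest row | 2/25 = 8.0% | 3/25 = 12.0% |
| Grade 3 or higher, grouped | 2/25 = 8.0% | 2/25 = 8.0% |
| Grade 3 or higher, largest row | 1/25 = 4.0% | 1/25 = 4.0% |

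The largest row therefore shows 8/16 = 50% to 12/16 = 75% of the grouped rate, and 4/8 = 50% of the grouped rate at Grade 3 or higher. Under the Table 1 coding the rows add to 5 for 4 patients, because one patient carries two terms. Exact (Clopper-Pearson) 90% intervals are 5.7% to 33.0% for 4/25 and 1.4% to 23.1% for 2/25.

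**Dependence on the term list.** Under the Table 1 coding, the second Grade 3 case is the proctitis. Neither Section 2.3.1.2 nor the examples in Table 11 name that term. If the list left it out, the grouped Grade 3 count would fall to 1/25. The list has to be fixed and cited for the figure to be reproducible.

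**Whether the SOC row helps.** Assuming that nausea is coded to the same gastrointestinal SOC, that row would be at least 14/25 = 56% from nausea alone (Protocol Table 3), so it cannot stand in for colitis.

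**Bone.** Protocol 2.3.1.1 reports that another drug of the class gave seven bone disorders in six of 94 patients (6/94 = 6.4%). The five thought related fall under four descriptions: osteoporosis, pathological fracture, osteopenia and spinal fracture. Adding events gives 7 for 6 patients. The two other disorders are not named, so no largest-row figure for all seven can be given.

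**Range under assumptions.** Module sizes are redacted. With an assumed 16 to 25 patients, a true grouped rate of 5% to 16%, one term per patient and an equal split over 2 to 4 terms, simulation puts the largest row at 52% to 87% of the grouped rate on average.

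**The case against.** The strongest reply is that the SAP breaks no commitment. Protocol 9.4.3.1 asks only for preferred term, SOC and severity, and the protocol defines AEPI as extra data capture, not as an analysis. Every term is tabulated by maximum grade, relatedness, seriousness and dose action, and every AE is listed by patient, so a reader could count the group by hand. The Phase 1 cases arose at starting doses of 3 mg and 10 mg, which this trial does not use, and Table 1 is not shown to contain MedDRA preferred terms. Module analyses are separate and descriptive, and the toxicity named for the 1 mg cohort is dysgeusia. For bone, part of SAP 4.12.4.6 is redacted, and the CRF Guidelines and table shells are not available.

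All of that stands. It limits the point to an improvement in presentation and makes the Phase 1 figures an illustration. It does not supply a grouped per-patient count or worst grade, and hand-counting from a listing without a cited term list is not a planned result.

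Several stronger readings are tempting but not supported:
- A reader might infer from the SAP revision history, "Revision of Adverse Events section (Outputs added, AEPI, Dysgeusia assessment", that an AEPI output was promised and then dropped. A change log describes superseded text and proves neither.
- A reader might infer that these harms would be hidden or under-reported. They would be split across rows, not omitted.
- A reader using Table 1 alone might say that the colitis row shows only half the cases and none at Grade 3. Section 2.3.1.2 codes the 10 mg case as Grade 3 colitis, so neither statement is settled.
- A reader might cite the two Phase 2 SAEs (enteritis and colitis) as splitting within this trial. The enteritis case was in study RXC004/0002.

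**Conclusion.** The gap is real and worth closing. The protocol collects both AEPIs as categories of terms and manages colitis events as a group, yet SAP 4.12.1 plans no grouped per-patient incidence or worst grade for either. In the documents' own Phase 1 data this is the difference between 16% and 8% to 12% for any intestinal inflammation, and between 8% and 4% at Grade 3 or higher.

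The size rests on three assumptions: that Phase 1 terms resemble the preferred terms this trial will record, that the 10 mg case is coded in one of the two ways the protocol gives, and that the term list covers it at Grade 3. Those two descriptions of the same patient differ and should be reconciled. For bone toxicity the absence of a grouped AE summary is visible in SAP 4.12.1, but its size cannot be judged from the documents.

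**What to change.** In SAP 4.12.1, cite the AEPI term lists in the CRF Guidelines by version. Because those lists are framed in CTCAE terms and the tables use MedDRA, state how the terms map to preferred terms.

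Then add, for each module and each Module 2 cohort, one table giving the number and percentage of patients with:
- at least one colitis event;
- at least one bone toxicity event.

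Each patient is counted once per group. Show both groups by worst grade, relatedness, seriousness and action taken (reduction, interruption, discontinuation). Give an exact confidence interval; 90% would match the level already used for response and disease control. Time to first onset is optional.

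The table should not be extended unchanged to the pembrolizumab Events of Clinical Interest in Protocol 12.10. Those are an overdose without symptoms and a liver-test threshold, which do not suit this layout, and SAP 4.12.3 already plans eDISH plots for liver toxicity.

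The cost is a short SAP amendment and the programming of one table layout. AE terms, grades and actions are already collected, and no dose or treatment rule is touched.
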